The two groups where both imaging modalities (CT and perfusion imaging) agree:

1. Unfavorable profiles on both: the results would not contribute to the comparison of imaging selection.
2. Favorable profile on both: there is, as detailed, strong evidence from RCTs supporting thrombectomy in both early and late time windows; thus randomizing these patients to compare imaging selection for thrombectomy is unethical and not feasible.

In SELECT 2, in order to compare the outcomes between imaging selection modalities, we propose to examine the correlation between the discordance in imaging profile and outcome rates, both functional independence as well as safety outcomes. We also propose to examine if there is a heterogeneity of treatment effect of thrombectomy in patients with discordant imaging profile (favorable CT/unfavorable perfusion imaging and unfavorable CT/favorable perfusion imaging).

Based on the SELECT trial results, patients with unfavorable CT/ favorable CTP had 48% good outcomes vs favorable CT/unfavorable CTP with 32% good outcomes (16% absolute difference). A superiority margin at 15% will be set between the two discordance groups and good outcome rates between patients with discordant imaging profiles will be compared. If those differences do not reach the statistical margin, then among patients with discordant imaging profile who met the inclusion criteria for SELECT 2 and treated with thrombectomy, the outcome rates did not differ.

In addition to comparing the rates of good outcomes between patients treated with thrombectomy in patients with discordant profiles, thrombectomy treatment effect heterogeneity will be assessed in patients with favorable CT/ unfavorable perfusion imaging and those with unfavorable CT/favorable perfusion imaging. If no heterogeneity exists, then thrombectomy benefit is not modified in the two scenarios when the two imaging modalities disagree.

1.6. Thrombectomy efficacy and safety in patients with favorable CT but unfavorable perfusion imaging profile

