3.1. Study Design

SELECT 2 is a prospective, multicenter, randomized open-label clinical trial evaluating: 1) the efficacy and safety of thrombectomy in patients with unfavorable imaging profiles (large core) on either CT or perfusion imaging or both treated within 0 to 24 hours from last-known-well; and 2) the correlation between CT and CT/MR perfusion imaging profiles and 90 day clinical outcomes (good mRS scores, 0-2) in LVO patients treated with thrombectomy within 0 to 24 hours from last-known-well.

On presentation to the EVT capable center enrolling patients in SELECT 2 trial, patients will receive a simple (non-contrast CT), CT angiography and CT/MR Perfusion with mismatch determination using automated RAPID software. The physicians will evaluate the CT scans and provide ASPECTS score. The CT image will also undergo processing by iSchemaView RAPID ASPECTS software as an investigational tool and the results will be available to the physicians for review. ASPECTS for patient selection will be determined independently by appropriately trained clinicians prior to any assessment with automated ASPECTS.

Patients with unfavorable imaging profiles on either CT (ASPECTS 3-5) or perfusion imaging (CTP: rCBF<30% or MRP: ADC <620 ≥50cc) or both within 0-24 hrs from last-known-well will be randomized into thrombectomy plus medical management vs medical management alone.

- Analysis 1: good outcomes rate in thrombectomy patients in Group 2 different to Group 1: 15% margin
- Analysis 2: heterogeneity of treatment effect of thrombectomy between Group 2 and Group 1
- Analysis 3: EVT superior to MM in patients with Favorable CT/Unfavorable CTP

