6.2. Statistical plan for the second aim

The second aim is to compare outcomes in patients with discordant imaging profiles. Good outcome rates (90-day mRS 0-2) will be compared between EVT patients with favorable CTP/unfavorable CT and EVT patients with unfavorable CT/favorable CTP. Logistic regression model will be applied and odds ratio as well as 95% CI will be calculated. If there is a significant difference in the outcome, we will evaluate whether any patient characteristics could be potential confounders and can explain these differences.

We will also assess the heterogeneity of the treatment effect of thrombectomy comparing to medical management between patients with favorable CT/unfavorable CTP and patients with unfavorable CT/favorable CTP. We will assess the heterogeneity by evaluating the interaction effect in the logistic regression model between treatment groups (EVT vs MM) and imaging profile (favorable CT/unfavorable CTP vs unfavorable CT/favorable CTP). If the interaction term is statistically significant, we will examine patient characteristics and other baseline clinical characteristics for possible correlations or confounding factors.

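### Aim 2A treats missing a 15-point margin as proof that outcome rates are the same, when the expected difference is 16 points and section 6.2 has no margin

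*Combined protocol and SAP*

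**What the plan says.** Section 1.5 takes the good-outcome rates (mRS 0-2 at 90 days) of the two discordant groups from the earlier SELECT cohort: 48% for unfavorable CT with favorable CTP, and 32% for favorable CT with unfavorable CTP. It then states "A superiority margin at 15% will be set between the two discordance groups", and gives the consequence of a miss: "If those differences do not reach the statistical margin, then among patients with discordant imaging profile who met the inclusion criteria" for the trial, "treated with thrombectomy, the outcome rates did not differ".

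Section 3.1 and section 19 both list this as Analysis 1: "good outcomes rate in thrombectomy patients in Group 2 different to Group 1: 15% margin". Neither gives a test, a direction or an alpha.

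Section 6.2, the statistical plan for this aim, has no margin and no rule for a miss: "Logistic regression model will be applied and odds ratio as well as 95% CI will be calculated". Its first paragraph describes the groups as "EVT patients with favorable CTP/unfavorable CT and EVT patients with unfavorable CT/favorable CTP", which is the same group twice. Its second paragraph names them correctly.

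For Aim 2B, section 1.5 says "If no heterogeneity exists, then thrombectomy benefit is not modified in the two scenarios". Section 6.2 offers only a test: "We will assess the heterogeneity by evaluating the interaction effect in the logistic regression model between treatment groups".

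**The concern.** There are three problems.

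1. **The inference is invalid.** Not reaching a superiority margin is not evidence that two rates are the same. With an observed difference of 14 points, the rule would still report that the rates were the same. At most, a miss says that a 15-point difference was not observed or not shown.
2. **The margin is one point below the expected effect.** The rule therefore fails often even when the sponsor's assumption is exactly right.
3. **Two different analyses are in the document.** Sections 1.5, 3.1 and 19 carry a margin on the absolute difference, while section 6.2 has an odds ratio against no effect. Nothing says which governs, so the choice could be made after the data are seen.

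Section 1.5 presents this comparison as the trial's way of comparing imaging selection modalities. A false finding of no difference would misstate the answer to that question.

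**Working it through.** **Inputs**
- Rates 48% and 32%, margin 15 points (section 1.5). The plan's own figure reproduces: 48 - 32 = 16 points.
- Maximum 560 patients (section 6.1) at 1:1 (section 3.4), so 280 thrombectomy patients.
- Group shares in section 6.1: Group 1 = 14% + 6% = 20% and Group 2 = 14% + 6% = 20%, so 0.20 × 280 = 56 per group.
- Alternative shares from SELECT (section 1.5, rounded): 8%, 7% and 4%, a total of 19%. This gives 280 × 8/19 ≈ 118 and 280 × 7/19 ≈ 103.
- Alpha is not stated for this aim. One-sided 2.5% is assumed, matching the 95% CI in section 6.2.

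**Standard error of the difference**

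SE = √(0.48 × 0.52/n1 + 0.32 × 0.68/n2)
- 56/56: 0.0913
- 118/103: 0.0650

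**Chance that a true 16-point difference is reported as no difference**

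Reading A, the observed difference must reach 15 points: 1 - Φ(0.01/SE).

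Reading B, 15 points is the null: 1 - Φ(0.01/SE - 1.96).

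| Group sizes | A, normal | A, exact | B, normal | B, exact |
|---|---|---|---|---|
| 56/56 | 45.6% | 46.2% | 96.8% | 96.3% |
| 118/103 | 43.9% | 43.7% | 96.5% | 96.1% |

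The exact columns enumerate the two binomial distributions. With a one-sided 5% bound, reading B gives about 93-94%. Under reading B, 80% power would need (0.2496 + 0.2176) × (1.96 + 0.8416)² / 0.01² ≈ 36,700 per group.

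**Early stopping and enrichment**
- 376 randomized, the average in scenario 1 of Table 3 (188 thrombectomy; 38/38 or 79/69): A 45-46%, B 97% (normal). The exact A at 38/38 is 44%.
- Accrual limited to Groups 1 and 2 after the first interim and run to 560 (20 + 90 = 110 per group, or 138/121 with SELECT shares): A 43-44%, B 96%.
- Stop at 200 (20/20): A 47% normal, 41% exact; B 97% and 96%.
- Accrual limited to Group 1 after the first interim (200/20): A 46% normal, 45% exact; B 97% and 94%.

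**Section 6.2's comparison against no difference**

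The log odds ratio is ln[(0.48 × 0.68)/(0.32 × 0.52)] = 0.674, with SE 0.392 (56/56) or 0.280 (118/103). The range in each line below runs from the risk-difference scale to the log-odds scale. Chance of a non-significant result:
- 56/56: 58-60%
- 118/103: 31-33%

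Section 6.2 does not label such a result as no difference.

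**Disagreement on the same data** (exact, Wald test of the log odds ratio at 1.96)
- Reading A, 118/103: odds ratio significant but observed difference under 15 points, 12%. At 56/56 this is about 0.01%.
- Reading A, 56/56: 15 points reached but odds ratio not significant, 14%.
- Reading B: odds ratio significant but margin missed, 36% (56/56) or 64% (118/103).

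No power is computed for the interaction, because the documents give no medical-management rate by discordant profile.

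**The case against.** The strongest reply is that section 1.5 is background and section 6.2 is the statistical plan. An analyst following section 6.2 would never apply the margin rule. This is partly right: the conclusion about a miss appears only in section 1.5. But sections 3.1 and 19 carry the margin into the design text, and nothing says that section 6.2 prevails.

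Other points carry some weight:
- The wording about reaching a margin most naturally describes the observed difference. The 96-97% figure needs the other reading and an assumed alpha. Calling it a superiority margin keeps that reading open.
- Disagreement under reading A is lopsided. A significant odds ratio with a missed margin is essentially absent at 56/56 and appears only with the SELECT shares. The 14% at 56/56 runs the other way, and section 6.2 attaches no claim of no difference to it.
- At 56/56, section 6.2's test misses a 16-point difference more often (58-60%) than reading A does (46%). The gain from relying on section 6.2 is an honest label, not better detection.
- For Aim 2B, section 1.5 speaks of heterogeneity not existing, not of a non-significant test. The misreading is possible but not written as a rule, so it is a lesser point.
- The duplicated group label is evidently a slip.

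None of this makes a missed margin evidence of equal rates.

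**Conclusion.** The concern holds. As written, section 1.5 can turn a true difference of the expected size into a reported finding of no difference. At full enrollment this happens in about 44-46% of trials under the observed-threshold reading and 96-97% with 15 points as the null. The figures assume true rates of 48% and 32%, 1:1 allocation and, for the second reading, one-sided 2.5%. They depend little on group size: the smaller or enriched cases checked give 41-47% and 94-97%.

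The consequence is confined to the second aim. It is wrong as written rather than missing detail, and should be corrected before the analysis.

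**What to change.** Reconcile sections 1.5, 3.1, 6.2 and 19 to one analysis:

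- Delete the rule that a missed margin means equal rates.
- Use section 6.2's comparison against no difference, and report the difference in mRS 0-2 rates with a 95% CI beside the odds ratio.
- State that a non-significant result is inconclusive.
- If the 15-point figure is kept, say whether it is the null or a threshold for the observed difference, give the alpha, and word a miss as a 15-point difference not having been shown.
- Claim similarity only under a separately prespecified equivalence criterion. A ±15-point rule with a 90% CI would have low power at 56 per group: under true equality, 17% at a common rate of 24%, 7% at 32% and under 1% at 48%.
- State that a non-significant interaction is not evidence that the benefit is unmodified.
- Correct the duplicated group label in section 6.2.

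The cost is protocol and SAP wording, with no extra patients. The price is a more modest conclusion. The 95% CI for the difference would be about ±18 points at 56/56 (1.96 × 0.0913) or ±13 points at 118/103 (1.96 × 0.0650), so an inconclusive result is likely at the smaller size.

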1.7. Rationale and use of iSchemaView RAPID and iSchemaView RAPID ASPECTS

iSchemaView RAPID: At the conclusion of the CT/MR Perfusion scan, the technologist sends the sequences from the console to RAPID for automated processing. The RAPID software was developed based on data from DEFUSE 1 and was prospectively validated in DEFUSE 2. The system provides fully automated processing of brain images. The RAPID output maps, which identifies the volume and location of ischemic core and perfusion lesions, are emailed to

investigators (protected health information is automatically removed) and auto-sent to PACS for viewing within 5 minutes of completion of the scan. Immediately after the images are available, the investigator will review the results of the RAPID mismatch map, simple (Non-contrast) CT and the CTA to determine assignment in the specified group. The accuracy of the software for identifying the size and location of perfusion and diffusion lesions has been established by extensive validation and testing on blood flow phantoms; the software received FDA 510K clearance for clinical use in 2013. The agreement between local investigators and the Imaging Core Lab for identification of the mismatch profile in DEFUSE 2¹⁵ was 97%, κ 0.92; 95% CI 0.83–1.0. Identification of core and penumbral volumes will be done in accordance with the procedures followed in DAWN⁶ and DEFUSE 3⁷ trials.

iSchemaView RAPID ASPECTS: Inter-rater reliability of ASPECTS score has been shown to be fair¹⁶. In a recent study, Automated ASPECTS has been shown to have a much higher agreement ($k = 0.896$) with the predefined gold standard sources (reporting of results by two board-certified neuroradiologists) compared to human readers ($k = 0.574$ and $k = 0.556$)¹⁷. The automated ASPECTS score is included as an investigational tool in the study. ASPECTS for patient selection will be determined independently by appropriately trained clinicians prior to any assessment with automated ASPECTS. In case of disagreements, ASPECTS scores provided by the clinicians will override the ASPECTS score by iSchemaView RAPID ASPECTS. In addition, the use of perfusion imaging in all patients will also help verify if a large core is present in these patients.

1.8. Rationale for including patients with extracranial ICA occlusion:

Patients with extracranial ICA occlusion, as of now, do not have a proven treatment for revascularization and the rates of recanalization achieved by the only currently FDA approved treatment, IV tissue plasminogen activator have been poor¹⁸⁻¹⁹. Another issue with these patients is the potential of so called “Pseudoextracranial occlusion.” In a significant proportion

of cases with intracranial ICA occlusion, because of low flow, the contrast used for obtaining CT angiogram does not reach the level of occlusion and thus the occlusion appears to be extracranial on the conventional CT angiogram²⁰. The only way to confirm the diagnosis of pseudoextracranial occlusion is to obtain an angiogram using fluoroscopy in the angio suite. Such cases form a significant number of patients presenting with extracranial occlusion who may benefit from the thrombectomy procedure, but are excluded from the trial based on the appearance on CT angiogram. Including cases with extracranial ICA occlusion on CTA will allow for enrollment of these patients. Randomized controlled trials such as ESCAPE and REVASCAT reported 40 (12.7%) and 31 (10.3%) patients with extracranial ICA occlusions. EXTEND-IA in early window and DEFUSE 3 in late time window also allowed for inclusion of patients with extracranial ICA, though did not report the number of patients enrolled with extracranial ICA.

2. Study Question, Aim, and Hypothesis

Study aims: are to evaluate in acute ischemic stroke patients due to a large vessel occlusion in the anterior circulation (MCA M1 and ICA):

- Primary aim: If thrombectomy plus medical management as compared to medical management alone will be efficacious and safe in patients with large core on either CT (ASPECTS 3-5) or perfusion imaging (CTP: rCBF<30% or MRP: ADC <620 ≥50cc), treated within 0-24 hours from last known well. We hypothesize that patients with unfavorable profiles (large core) treated with thrombectomy on either imaging modality will have significantly better outcomes than large core patients treated with medical management only.
- Second aim: The second aim is to look at the correlation of imaging profiles with thrombectomy clinical outcomes and treatment effect. It will be evaluated by comparing the outcomes in patients with discordant imaging profile and assessing if thrombectomy outcome rates and treatment effect will differ in patients with

discordant imaging profiles (favorable CT/unfavorable perfusion imaging and unfavorable CT/favorable perfusion imaging).

- A) Evaluate good clinical outcome (90-day mRS 0-2) rates in patients with discordant imaging profile (unfavorable CT/favorable perfusion imaging vs favorable CT/unfavorable perfusion imaging) treated with thrombectomy.
- B) Evaluate the heterogeneity of thrombectomy treatment effect in patients with favorable CT/unfavorable perfusion and unfavorable CT/favorable perfusion imaging.

[figure not shown]
[figure not shown]
3. Methods

3.1. Study Design

SELECT 2 is a prospective, multicenter, randomized open-label clinical trial evaluating: 1) the efficacy and safety of thrombectomy in patients with unfavorable imaging profiles (large core) on either CT or perfusion imaging or both treated within 0 to 24 hours from last-known-well; and 2) the correlation between CT and CT/MR perfusion imaging profiles and 90 day clinical outcomes (good mRS scores, 0-2) in LVO patients treated with thrombectomy within 0 to 24 hours from last-known-well.

On presentation to the EVT capable center enrolling patients in SELECT 2 trial, patients will receive a simple (non-contrast CT), CT angiography and CT/MR Perfusion with mismatch determination using automated RAPID software. The physicians will evaluate the CT scans and provide ASPECTS score. The CT image will also undergo processing by iSchemaView RAPID ASPECTS software as an investigational tool and the results will be available to the physicians for review. ASPECTS for patient selection will be determined independently by appropriately trained clinicians prior to any assessment with automated ASPECTS.

Patients with unfavorable imaging profiles on either CT (ASPECTS 3-5) or perfusion imaging (CTP: rCBF<30% or MRP: ADC <620 ≥50cc) or both within 0-24 hrs from last-known-well will be randomized into thrombectomy plus medical management vs medical management alone.

- Analysis 1: good outcomes rate in thrombectomy patients in Group 2 different to Group 1: 15% margin
- Analysis 2: heterogeneity of treatment effect of thrombectomy between Group 2 and Group 1
- Analysis 3: EVT superior to MM in patients with Favorable CT/Unfavorable CTP

3.2. Enrollment Inclusion and Exclusion Criteria

Adult patients with AIS due to LVO in the anterior circulation (ICA and MCA occlusions in the M1 segment) who are normal or with minimal deficits at the time of their strokes (mRS 0-1), have received the pre-specified imaging profile (NCCT, CTA and CTP/MRP) prior to the treatment decision, and will be treated with thrombectomy (groin puncture time) plus medical management or medical management alone within 24 hrs from their last-known-well are eligible for the study (Table 1). A screening log of all patients with LVO presenting within 24 hours of symptom onset who receive thrombectomy, in addition to non-enrolled patients who qualify for SELECT 2 large core definition on imaging, will be kept. Clinical data will be collected to evaluate which method best correlates with patient outcome after thrombectomy. Mechanical thrombectomy includes the use of stent retrievers (e.g. Trevo[®], Solitaire[®], EmboTrap Revascularization Devices) and/or aspiration devices (e.g. MicroVention SOFIA Catheter, and Penumbra) as recommended by AHA (American Heart Association) guidelines. Please review Appendix C for a list of all approved devices.

Table 1. The SELECT 2 study inclusion and exclusion criteria

Inclusion Criteria	
 1) Adults (18-85 years) with the final diagnosis of an acute ischemic stroke 2) NIHSS \geq 6 3) Last known well to groin puncture or medical management between 0 to 24 hours 4) Pre-stroke modified Rankin Scale score of 0-1 5) Eligible for thrombectomy or medical management 6) Signed Informed Consent obtained 7) Subject willing to comply with the protocol follow-up requirements 8) Anticipated life expectancy of at least 3 months
---------------------------	---

Exclusion Criteria	
1) Inability to undergo CT-Angiography and/or CT/MR Perfusion imaging (e.g., renal insufficiency, iodine/contrast allergy)2) Co-morbid psychiatric or medical illnesses that would confound the neurological assessments3) Treatment with IV thrombolytic therapy beyond 4.5 hours from last known well4) Treated with IV thrombolytic therapy 3-4.5 hours after last known well AND any of the following:
- age >80- current anticoagulant use- history of both diabetes AND prior stroke- NIHSS >25- ischemic involvement of more than third of the MCA territory5) Current participation in another investigational drug or device study.
---------------------------	---

3.2.1.1. Specific Neuroimaging Inclusion Criteria

1. Proven large vessel occlusion in ICA or MCA-M1 occlusion (carotid occlusions can be cervical or intracranial, with or without tandem MCA lesions) determined by MRA or CTA
2. Large infarct-core lesion on at least one of the following
 - 2.1. Non-Contrast CT (ASPECTS of 3-5)*,
 - 2.2. CT perfusion (rCBF<30% ≥50cc),
 - 2.3. MRI-DWI (ADC<620 ≥50cc),

**ASPECTS 0-2 are not included in this study due to the expected poor outcome in these patients.*

3.2.1.2. Specific Neuroimaging Exclusion Criteria

1. Patients who have both ASPECTS of 6-10 on non-contrast CT **AND** core volume <50 cc on perfusion imaging
2. Patients with very large core on imaging on non contrast CT i.e. ASPECTS ≤ 2

3. Evidence of intracranial tumor (except small meningioma) acute intracranial hemorrhage, neoplasm, or arteriovenous malformation
4. Significant mass effect with midline shift
5. Evidence of internal carotid artery dissection that is flow limiting or aortic dissection
6. Intracranial stent implanted in the same vascular territory that precludes the safe deployment/removal of the neurothrombectomy device
7. Acute symptomatic arterial occlusions in more than one vascular territory confirmed on CTA/MRA (e.g., bilateral MCA occlusions, or an MCA and a basilar artery occlusion).
8. Signs of established infarct and large area of cerebral edema on non-contrast CT

